1.1 Risks to Subjects

a. Human Subjects Involvement and Characteristics:

Totally, up to 50 veterans with comorbid ADHD and PTSD will be recruited for this pilot clinical trial. All subjects will be Veterans from Operation Iraq Freedom / Operation Enduring Freedom (OIF/OEF). Our record review showed age range from 20 to 60 in this OIF/OEF group, and statistically they have fewer confounding variables for this clinical trial, including medical conditions such as hypertension or glaucoma (described detail in exclusion criteria) and cognitive impairments such as dementia, which meet criteria for our research study. PTSD subjects with and without ADHD cognitive symptoms will be recruited from the Charleston VAMC Mental Health Service Line. Examining and treatment of ADHD cognitive symptoms among Veterans with PTSD is scientifically and ethically justified to further understand the mechanism of developing PTSD after trauma exposure, and what is the best treatment for Veterans with comorbid PTSD and ADHD. Specific inclusion and exclusion criteria are listed below:

Inclusion Criteria: 1) OIF/OEF Veterans age 20 to 60 with PTSD and significant ADHD symptoms (CAARS-S:S > 65); 2) Good physical health. 3) Trauma exposure sufficient to meet Category A of PTSD criteria (Breslau and Kessler 2001)

Exclusion Criteria: 1) Age younger than 20 or greater than 60. 2) Known sensitivity to ATX 3) Presence of disorders that could conceivably be exacerbated by atomoxetine (specifically, narrow angle closure glaucoma, urinary outflow obstruction, hypertension, and neurological disorders, particularly tics and Tourette's syndrome, or a history of epilepsy or seizures). 4) use of concomitant medication that could potentially interact with atomoxetine including monoamine oxidase inhibitors (MAOI), antihypertensive medication, or any concomitant medication that was a cytochrome 2D6 inhibitor (CYP2D6), since atomoxetine's elimination involves the CYP2D6 system. 5) An active or lifetime major mental health diagnosis as determined by DSM-IV Axis I Disorders, including schizophrenia, schizoaffective disorder, psychotic disorder not otherwise specified, bipolar I disorder, bipolar II disorder, bipolar disorder not otherwise specified. The project will allow presence of depressive disorders if the depressive episodes are secondary to PTSD. 6) Current substance dependence and abuse (within 3 month). 7) Females who are pregnant. 8) Suicidal thoughts and behavior.

b. Sources of Material

c. Potential Risks

Therapeutic Risk:

Pharmaceutical agent: Atomoxetine (ATX) is a norepinephrine reuptake inhibitor that blocks norepinephrine and dopamine transporters and increases dopamine and norepinephrine availability in the synaptic cleft at the pre-frontal cortex. ATX is one of the first line treatments for children and adult attention deficit hyperactivity disorder (ADHD). Efficacy and safety of ATX are well established by numerous clinic trials in the past 15 years. However, there have been no trials of ATX for treating ADHD cognitive complaints associated with PTSD, possibly because of the less awareness of high comorbid rate of ADHD and PTSD, and concern about the abuse potential of commonly used stimulant medications and concern about interventions that increase catecholamine release may exacerbate

anxiety symptoms. Currently, ATX is the only non-stimulant medication approved by FDA for treatment of ADHD. Studies have shown that ATX is safe, effective, and well tolerated with mild side effects profile in acute and long-term treatment of ADHD in children, adolescent, and adult (reviewed by Vauphan et al, 2009). Unlike psycho-stimulants, ATX does not show abuse potential (Bymarster et al 2002). A couple of studies have also shown efficacy of ATX in treatment of ADHD cognitive symptoms in patients with comorbid ADHD and anxiety and/or depression. ATX were very well tolerated in individual with comorbid ADHD and anxiety, or ADHD and depression (Geller et al, 2007; Deviss, 2008). There is not excessive anxiety or other symptoms among subjects with comorbid anxiety and depression, who were taking ATX. Although ATX has not been tested in PTSD, a similar selective norepinephrine reuptake inhibitor, reboxetine has been studied in PTSD and shown safety and efficacy in reducing PTSD symptoms in motor vehicle accident related PTSD (Spivak et al 2006). The above literature review provides strong rationale for choosing ATX to treat cognitive symptoms in Veterans with ADHD/PTSD.

Adverse Effects:

Common

- **Cardiovascular:** Increased diastolic arterial pressure (adult, 4.8% to 12.6%; pediatric, 9.3% to 21.5%), Increased systolic arterial pressure (adult, 4.2% to 12.4%; pediatric, 4.9% to 12.5%), Tachycardia (adult, 1.5% to 22.4%; pediatric, 0.3% to 23.4%)
- **Endocrine metabolic:** Weight decreased (adults, 2%; pediatric, 7.1% to 29.1%)
- **Gastrointestinal:** Abdominal pain (adult, 7%; pediatric, 17% to 18%), Constipation (adult, 8%; pediatric, 1% to 2%), Decrease in appetite (adult, 16%; pediatric, 16%), Nausea (adult, 26%; pediatric, 7% to 13%), Vomiting (adult, 4%; pediatric, 11%), Xerostomia (adult, 20%)
- **Neurologic:** Headache (pediatric, 19%), Insomnia (adult, 15%; pediatric, at least 2%), Somnolence (adult, 8%; pediatric, 11%)
- **Renal:** Delay when starting to pass urine (adult, 6%)
- **Reproductive:** Dysmenorrhea (adult, 3%), Erectile dysfunction (adult, 9%)
- **Other:** Menopausal flushing (adult, 3%)

Serious:

- **Cardiovascular:** Myocardial infarction, Prolonged QT interval, Sudden cardiac death
- **Hepatic:** Injury of liver (Severe), Liver failure
- **Neurologic:** Cerebrovascular accident, Dyskinesia, Seizure (adult, 0.1%; pediatric, 0.2%)
- **Psychiatric:** Mania, Psychotic disorder, Suicidal thoughts (pediatric, 0.4%)
- **Reproductive:** Priapism (rare)
- **Other:** Angioedema

Contraindications

- cardiac or vascular disorders, severe; at risk for deterioration with clinically important increase of blood pressure (15 to 20 mm Hg) or heart rate (20 beats per minute); monitoring recommended.
- hypersensitivity to atomoxetine or to other components of the product.
- MAO inhibitor use; do not administer atomoxetine during therapy with or within 2 weeks of discontinuing an MAO inhibitor; do not administer MAO inhibitor within 2 weeks of discontinuing atomoxetine.
- narrow angle glaucoma; increased risk of mydriasis
- pheochromocytoma, current or history of; increased risk for serious reactions, including tachyarrhythmia and elevated blood pressure.

Psychological Risks: There is a minor chance that participant will experience anxiety, discomfort or embarrassment during the data collection process, the investigational team will make every effort to minimize potential psychological risks by maintaining a pleasant and professional manner, conducting interviews and physical assessments in a private clinical office, encouraging dialogue regarding the research process, and allowing participants to discuss any reactions or feelings that they may have throughout study participation. Additionally, in order to avoid or minimize any further discomfort, the participants are allowed to take breaks during the interviews and assessment, or reschedule the

appointment for completion at a later time. Participants can refuse to answer any question during an interview or on the questionnaire if it makes the participant uncomfortable.

Legal, Social and Economic Risks: In order to prevent the risk of developing feelings of being “labeled” or “stigmatized”, participants will be ensured that confidentiality safeguards will be strictly maintained throughout the study. Such safeguards include the conduction of all interviews and clinical visits within private and secure areas or offices. Additionally, all study documents will be kept in a locked office or on a computer located in a secure area, with limited password access. Confidential hospital medical records will document participation in the study through mental health progress notes. Additionally, participants’ name will not be identified in the data analysis, publications, or presentations of the research results. A Health Insurance Portability and Accountability Act (HIPAA) authorization page is included with the informed consent to notify the participants of the use of identifiable personal health information. The informed consent and HIPAA authorization page provide a detailed outline of the provisions utilized to protect the confidentiality of research data. The methods used to obtain information about the participants include medical record review and assessments described above.

In order to minimize any economic risk related to having to miss work or having to pay for transportation to and from the research visits, the study team will coordinate with the participants to schedule appointments at the most convenient time, including seeing participant outside working hours and limiting the frequency of visits to those necessary to adhere to the protocol.

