Adverse effects (AE): Typical adverse events reported significantly more frequently with atomoxetine than placebo included dry mouth, insomnia, nausea, decreased appetite, constipation, dizziness, sweating, dysuria, sexual problems and palpitations. Modest increases in heart rate and blood pressure were well tolerated and gradually decreased on cessation of treatment.

Contraindications: ATX is contraindicated in patients known to be hypersensitive to the drug and during treatment with monoamine oxidase inhibitors (hypertensive crises may result). Medication will be stored and dispensed from the Charleston VAMC investigational drug pharmacy. Records will be maintained of all doses dispensed, and Veterans will be asked to return all unused tablets and empty prescription vials to the clinic for assessment of treatment compliance.

C3. Method

Subject Recruitment: All the subjects will be recruited through Charleston VAMC Mental Health Service Line. The Charleston VAMC has a large base of potential comorbid PTSD and ADHD participants. Many clinical trials, including pharmaceutical and psychotherapeutic trials are currently conducted in conjunction with the Charleston VAMC PTSD Clinical Team (PCT) clinic and the PCT team receives numerous PTSD evaluation consults from OIF/OEF program and Primary Care. Currently the PCT clinic receives 200 to 250 new referrals yearly of OIF/OEF Veterans who meet full criteria for PTSD based on a comprehensive initial intake interview that includes CAPS and functional impairment assessments. PI, [name] currently manages pharmacological consults for OIF and OEF Veterans. A HIPAA waiver of authorization will be on file with the IRB giving the research team permission to recruit from prior study populations. Veterans with PTSD from OIF/OEF are uniquely suited for this study because statistically they have fewer confounding variables for this clinical trial, including medical conditions such as hypertension or glaucoma and cognitive impairments such as dementia. Interested veterans who participate in clinical trials are explained the nature, purpose, and procedure of the study and asked to sign an informed consent that will explain in detail the purpose of the study, potential risks and benefits of pharmacotherapy study participation and alternative treatments that may be available.

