Inclusion Criteria: 1) OIF/OEF Veterans age 20 to 60 with PTSD and significant ADHD symptoms (CAARS-S:S > 65); 2) Good physical health. 3) Trauma exposure sufficient to meet Category A of PTSD criteria (Breslau and Kessler 2001)

Exclusion Criteria: 1) Age younger than 20 or greater than 60. 2) Known sensitivity to ATX. 3) Presence of disorders that could conceivably be exacerbated by atomoxetine (specifically, narrow

angle closure glaucoma, urinary outflow obstruction, hypertension, and neurological disorders, particularly tics and Tourette's syndrome, or a history of epilepsy or seizures). 4) use of concomitant medication that could potentially interact with atomoxetine including monoamine oxidase inhibitors (MAOI), antihypertensive medication, or any concomitant medication that was a cytochrome 2D6 inhibitor (CYP2D6) as atomoxetine's elimination involves the CYP2D6 system. 5) An active or lifetime major mental health diagnosis as determined by DSM-IV Axis I Disorders, including schizophrenia, schizoaffective disorder, psychotic disorder not otherwise specified, bipolar I disorder, bipolar II disorder, bipolar disorder not otherwise specified. The project will allow presence of depressive disorders if the depressive episodes are secondary to PTSD. 6) Current substance dependence and abuse (within 3 month). 7) Females who are pregnant or likely to become pregnant. 8) Active suicidal thoughts and behavior.

Suicide Screen: A screen for recent or current suicidal thought and/or attempts will be conducted before the interview. If a subject reports suicidal thought at the time of interview, his physician or psychiatrist will be informed and the subject will be escorted to the ER immediately for further evaluation and treatment.

Screening/Baseline Evaluation: During this visit subjects will review and sign the Informed Consent. Eligibility to participate in this portion of the study will be determined by a minimum 6-month duration of PTSD illness, CAARS-S:S score of 65 or higher as well as a positive ADHD score for the adult section of the Conners ADHD interview, a total CAPS severity score of 55 or higher at the baseline visit. If the subjects qualify, then a medical/psychiatric history will be obtained along with laboratory safety measures, including electrocardiogram (EKG), liver and renal panel (SMA-12), complete blood count with differential, urine toxicology screen and concomitant meds. If the veteran is female, urine pregnancy test will be obtained.

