PTSD Medication Stabilization: Those patients meeting inclusion criteria will be asked to maintain medications at current dosages where medically possible. Participants who have not initiated new prescription medications in the previous 4 weeks will initiate treatment one week following the assessment battery. However, those potential participants who have recently begun trials of prescription medication will be required to wait 4 weeks post-assessment to ensure medication stabilization, at which point the assessment battery will be re-administered.

Efficacy Assessments and Outcome Measurement: Primary outcome measures will be conducted at baseline and all subsequent visits by a qualified research clinician using the CAARS-S:S, with the Barkley Adult ADHD Rating Scale-IV (BAARS-IV) and Adult ADHD Quality of Life-29 (AAQoL-29) conducted at follow up visits. Clinical Global Impression Severity (CGI-S, at baseline only) and Clinical Global Impression Improvement (CGI-I, at all visits except baseline and W1) will be done as well. Additional assessments for evaluating secondary outcomes will include the Clinician Administered PTSD Scale (CAPS), Hamilton Depression Scale (HAM-D). Quality of life will be assessed using the Veteran's version of the Medical Outcomes Study 36-Item Short-Form Health Survey (SF36-V). In addition to subjective measures, the response inhibition task Go/NoGo (GNG) and Stop Signal (SST) will be used as objective assessments to measure ATX treatment outcomes.

Key Assessment Measures:

Mini-International Neuropsychiatric Interview (MINI, Sheehan et al., 1998): The MINI is an abbreviated structured psychiatric interview that takes approximately 10-20 minutes to complete. The MINI has shown good inter-rater reliability and test-retest reliability for screening psychiatric disorders.

CAADID Part II: Diagnostic Criteria (CAADID, Epstein et al., 2001) The CAADID is a structured interview that assists in the process of diagnosing adult ADHD. This assessment is appropriate for those 18 and older. It is most effective when used with other types of ADHD measures, such as the CAARS™.

Clinician Administered PTSD scale (CAPS, Weathers et al., 2000): The CAPS is a structured interview that assesses both frequency and intensity of PTSD symptoms according to DSM-IV criteria. It provides both a dichotomous index for PTSD diagnoses and a continuous index of PTSD symptom severity.

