1.2. Adequacy of Protection Against Risks

a. Recruitment and Informed Consent

Subjects will be recruited from Charleston VAMC OIF/OEF Screening Clinic. Additionally, Veterans with or without PTSD may be recruited through Savannah CBOC referrals if Charleston VAMC does not have a sufficient number of participants. The study will be open to all Veterans from Iraq Freedom Operation and Afghanistan who meet eligibility criteria regardless of ethnicity, gender or socioeconomic status. No charge will be incurred for the participant for any aspect of this study. Written consent will be obtained for each participant who meets the inclusion criteria prior to assessment. Veterans will be given as much time as needed to make a decision whether to participate. All participants will be informed that their participation is voluntary, and that reluctance to participate will not compromise availability of care, or the eligibility to participate in other studies. Participants may discontinue assessment at any time during the study.

b. Protection against Risk

Potential risks involve loss of time at work and the psychological stress involved in assessment procedures. These risks will be minimized in several ways. Breaks and encouragement will be given as needed during testing procedures. There is some flexibility in the on site assessment schedule to allow for completion of measures not finished during the scheduled testing time. In addition, some weekend/holiday assessment times will be offered to minimize loss of time of participants.

ATX is a widely used treatment for ADHD. It is generally well tolerated clinically. Subjects who meet the contraindications for ATX listed in section “Therapeutic Risk” will be excluded. Common side effects of ATX are dry mouth, insomnia, nausea, decreased appetite, and sweating. Insomnia and sweating are of some concern for individuals with PTSD; however, as noted above the ATX has been safely used in comorbid ADHD and anxiety. Subjects can also withdraw at any time without penalty.

The risk of venipuncture is minimal. The mild discomfort of venipuncture and very low possibility of local infection will be minimized by using experienced phlebotomists and standard blood drawing techniques. Universal precautions for the handling of human blood developed by the Centers for Disease Control will be followed at all times when working with blood as well as DNA isolated from blood.

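### The numbered exclusion lists do not carry all the atomoxetine contraindications that the protocol says will exclude a subject: one of five is absent and two are only partly covered

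*Combined protocol and SAP*

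**What the plan says.** Section 1.2 b (Protection against Risk) makes a commitment: "Subjects who meet the contraindications for ATX listed in section “Therapeutic Risk” will be excluded". The list it points to, under Contraindications in section 1.1 c, has five entries: severe cardiac or vascular disorders, hypersensitivity, MAO inhibitors, narrow angle glaucoma, and pheochromocytoma. The MAO inhibitor entry includes a time window: "do not administer atomoxetine during therapy with or within 2 weeks of discontinuing an MAO inhibitor". The last entry covers past as well as present disease: "pheochromocytoma, current or history of; increased risk for serious reactions".

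Eligibility is set out in two numbered lists, one in C3 (Method) and one in 1.1 a, with the same content on these points. Item 2 excludes known sensitivity to ATX. Item 3 begins "Presence of disorders that could conceivably be exacerbated by atomoxetine (specifically, narrow" and goes on to angle closure glaucoma, urinary outflow obstruction, hypertension and neurological disorders. Item 4 excludes interacting concomitant medication, naming MAO inhibitors, antihypertensives and CYP2D6 inhibitors. The inclusion criteria require good physical health without defining it.

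C2 (Investigational Agent) has a third and shorter statement: "ATX is contraindicated in patients known to be hypersensitive to the drug and during treatment with monoamine oxidase inhibitors".

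**The concern.** The protocol promises to exclude on five contraindications, but the lists written for screening do not name them all. Someone who works only from the numbered criteria could pass a patient with a history of pheochromocytoma, or one who stopped an MAO inhibitor a few days earlier, although 1.1 c and 1.2 b together say that this patient is excluded. What is at stake is patient safety, and consistency about who is eligible. The protocol itself names the hazards: hypertensive crisis with MAO inhibitors in C2, and tachyarrhythmia and raised blood pressure with pheochromocytoma in 1.1 c.

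**Working it through.** The plan states no figure on this point, so there is none to reproduce. The check is an item-by-item comparison followed by a day count.

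**Step 1. Contraindications in 1.1 c against the numbered criteria in C3 and 1.1 a**

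| Contraindication in 1.1 c | Numbered criteria | Coverage |
|---|---|---|
| Hypersensitivity | Exclusion 2, known sensitivity to ATX | Carried |
| Narrow angle glaucoma | Exclusion 3 | Carried |
| MAO inhibitor, current or stopped within 2 weeks | Exclusion 4, concomitant use only | Partial: no interval since stopping |
| Severe cardiac or vascular disorder | Exclusion 3 (hypertension), exclusion 4 (antihypertensives), inclusion 2 (good physical health) | Partial |
| Pheochromocytoma, current or past | None | Absent |

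The count is 2 carried + 2 partial + 1 absent = 5.

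**Step 2. Does another rule supply the MAO inhibitor interval?** The PTSD Medication Stabilization paragraph in C3 asks whether a new prescription drug was started in the previous 4 weeks; it does not ask about drugs that were stopped. A patient with no new drug "will initiate treatment one week following the assessment battery". The good-health criterion does not address drug history. No explicit rule supplies the interval.

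**Step 3. Does the schedule supply it in practice?** Inputs:
- *d* = days from stopping the MAO inhibitor to the assessment battery. The worst case for a patient no longer taking it at assessment is *d* = 0 (assumption).
- *w* = 7 days from battery to start of treatment (C3, PTSD Medication Stabilization).
- *L* = placebo lead-in before active drug: 6 days of placebo in week 1 (C1), or 7 if the whole week counts. *L* = 0 if the one-week wait is itself the lead-in.
- Interval stated in 1.1 c: 2 weeks = 14 days.

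Interval to first ATX in the ATX-first group = *d* + *w* + *L*. With *d* = 0:
- Lead-in of 6 days after the wait: 0 + 7 + 6 = 13 days, 1 day short.
- Lead-in of 7 days after the wait: 0 + 7 + 7 = 14 days, no shortfall.
- The wait is the lead-in: 0 + 7 + 0 = 7 days, 7 days short.

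Table 1 favours the first two. It shows a separate screening/baseline visit, with first dispensing at the W1 visit, and C1 makes week 1 the lead-in and weeks 2 to 5 the treatment weeks.

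Two groups meet the interval on any reading. Placebo-first patients reach ATX in week 7 instead of week 2, which is 5 × 7 = 35 days later: 7 + 35 = 42 to 14 + 35 = 49 days. Patients who recently began another drug wait 4 weeks = 28 days after the first assessment, which already exceeds 14.

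**The case against.** The strongest reply is that 1.2 b is itself an exclusion rule. It adds to the numbered lists, nothing in those lists admits a contraindicated patient, and the protocol read as a whole excludes all five conditions. No document says that screening uses the numbered lists alone. On this view the defect is one of cross-referencing. That is a fair description of its kind, but it does not remove the problem. Section 1.1 a introduces its list as the specific criteria, the commitment in 1.2 b appears in neither list, and the word *specifically* narrows the broad opening of item 3 to the named disorders.

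The reply is also right that the shortfall in the MAO inhibitor interval needs an unfavourable case. A current user is already excluded by item 4, and C3 asks patients to keep current medication unchanged where possible. It is right too that C2 describes the drug and is not an eligibility list, so its brevity adds little beyond a need for consistent wording.

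A reader might also infer that the safety work-up comes too late to affect eligibility, because C3 says "If the subjects qualify, then a medical/psychiatric history will be obtained along with laboratory safety measures". The documents do not support that. Table 1 places laboratory tests, EKG and concomitant medications at screening/baseline, before the first dispensing at W1. Several exclusions (seizure history, lifetime diagnoses, concomitant drugs, pregnancy) rely on that work-up. Testing after the rating scales is ordinary staged screening.

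**Conclusion.** The mismatch is real and should be corrected. Sections 1.1 c and 1.2 b exclude on five contraindications; the numbered lists carry two, cover two in part and omit one. The MAO inhibitor interval and pheochromocytoma are the clearest gaps, because no numbered criterion names either.

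Three stronger readings go beyond the text:
- That two contraindications are missing altogether. Severe cardiac or vascular disease is partly reached through hypertension, antihypertensive medication and the good-health criterion.
- That the schedule leaves only a week between an MAO inhibitor and ATX. Seven days is the less likely reading; 13 to 14 days fits Table 1 better, and the question arises only for ATX-first patients.
- That different sites would admit different patients. This is essentially one centre, with referrals from a second clinic if needed, so the risk lies in which text the screening staff use.

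The conclusion assumes that staff may screen from the numbered lists without going back to 1.1 c and 1.2 b. The documents give no frequency for recent MAO inhibitor use or for the conditions concerned, so the number of patients affected cannot be estimated and may be small. No statistical figure in the plan changes.

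**What to change.** Reconcile the exclusion lists in C3 and 1.1 a with the contraindications in 1.1 c and the commitment in 1.2 b, and align the shorter statement in C2. One eligibility list should agree with 1.2 b on all five entries, including the interval since stopping an MAO inhibitor. If the sponsor does not intend all five to exclude, 1.1 c and 1.2 b should be amended instead. Which clinical rule applies is for the sponsor to decide. The timing of history, EKG and laboratory tests need not change for this purpose.

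The cost is a wording amendment and a matching screening checklist, using information already collected at baseline. The downside is an occasional additional screen failure.
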